1 PROTOCOL SYNOPSIS

Title: Rates of MM synechiae formation post ESS: a double-blind randomized controlled study comparing Silastic and the Restora™ steroid eluting MM spacer

Primary Objective:

This study is designed to evaluate basic device usability and confirm safety and effectiveness of the Restora™ Steroid eluting spacer as compared to a Silastic spacer.

Background/ Rationale:

Endoscopic sinus surgery (ESS) is the gold standard surgical intervention for chronic rhinosinusitis that is not adequately controlled with maximal medical therapy.

In some patients, underlying inflammation (discharge, edema and polyposis), compounded by inflammation caused by surgical trauma may lead to an uncontrolled healing response, which results in the synechiae formation in the middle meatus (MM).

Incidence of synechiae formation varies in literature and ranges between 4-35%. Presence of middle meatal synechiae can impair sinus drainage, promote sinusitis, and limit endoscopic visualization of the sinus cavities postoperatively. This may result in difficulty in performing postoperative routine endoscopic debridement and examination, which is paramount to a successful outcome from ESS. Spacers are often inserted during surgery between nasal mucosal surfaces to prevent synechiae.

The aim of this study is to see if a steroid-impregnated spacer is more effective at reducing inflammation after sinus surgery than a Silastic spacer.

Study Population: Patient suffering from chronic rhinosinusitis in need of ESS

Number of Centers: 2-3

Number of Subjects:

A total of 49 patients will be treated.

Test article:

Restora Spacer material loaded with Mometasone Furoate

Study Design:

This is a double-blind randomized controlled study of 49 patients with chronic rhinosinusitis that require ESS.

Screening

In the screening period, inclusion/exclusion criteria for the study participation will be checked. Subjects who satisfy these criteria will be invited to participate in the study. Their consent will be recorded. As a standard of

care, all patients will fill out the validated SNOT-22 quality of life outcome questionnaire at this pre-op visit.

Blinding

The study will be double-blinded. Each patient will be his or her own control. The Silastic spacer will be placed on one side and the steroid-eluting spacer will be placed on the other. Neither the patient nor the assessor will know on which side the respective spacer is placed. The PI at the primary site will be the blinded assessor.

Procedure and follow up

Patient will undergo ESS and the spacers will be placed in the operating room upon procedure completion. Subjects will return to clinic after 6-8 days to have the spacers removed. The removed spacer materials will be shipped to SinuSys for residual steroid content analysis. After the initial visit, patients are seen again in clinic at 35 and 90 days postoperatively. At each visit endoscopic videos will be collected to enable scoring, as detailed in the endpoint section below. As a standard of care all patients are treated with oral antibiotics (Clavulin or Clindamycin if allergic to Penicillin) while they have spacers inserted into their nose.

The detailed study schedule is provided in Appendix A.

Projected Study Timelines

Anticipated Total Study Duration: Enrollment – 1-2 months, Follow up 3 months.

Study Endpoints

- **Primary Endpoint**
 - 35 day sinonasal mucosal inflammation assessed by rigid endoscopy and graded on Lund-Kennedy sinus mucosal endoscopic staging system
- **Secondary Endpoints**
 - 90-day sinonasal mucosal inflammation assessed by rigid endoscopy and graded on Lund-Kennedy sinus mucosal endoscopic staging system
 - 35 and 90-day intraocular pressure (IOP) assessed using applanation tonometry and compared to baseline IOP obtained preoperatively
 - 35 and 90-day post ESS incidence of middle meatal synechiae
 - 90-day Sinonasal Outcomes Test-22 (SNOT- 22) scores
 - 35-day frequency of postoperative interventions, including lyses of adhesions and debridement.
 - 35-day frequency of oral steroid rescue
 - 35 days middle turbinate position

Inclusion Criteria

- 1) Age between 18 and 75 years
- 2) Diagnosis of chronic rhinosinusitis (CRS), per current guidelines
- 3) Patients who need to undergo primary bilateral complete endoscopic sinus surgery
- 4) Subject has the ability to follow the study instructions, is willing to be available on the specific required study visit days, and is willing to complete all study visit procedures and assessments

5) Subject must understand the research nature of this study and sign an informed consent prior to the performance of any study-specific procedure or assessment

Exclusion Criteria

- 1) Subject is pregnant or breast feeding
- 2) Patients with sino-nasal tumors
- 3) Patients solely undergoing nasal septal reconstruction
- 4) Patients with previous history of endoscopic sinus surgery
- 5) Cystic fibrosis or syndromic patients
- 6) Patients with autoimmune diseases
- 7) Patients who have taken oral steroids less than 30 days prior to surgery
- 8) Patients with a history or diagnosis of glaucoma or ocular hypertension
- 9) Any other circumstance or condition that in the Investigator's opinion causes the subject to be an inappropriate candidate for participating in this study

Statistical Consideration

This study is designed to evaluate basic device usability and confirm safety and effectiveness of Steroid Impregnated Spacer. There is no success criteria set based on statistical calculation.

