8 STUDY DESIGN AND ENDPOINTS

Approximately 50 patients will receive spacers during their ESS procedures and be followed for 90 days. This will require enrolling approximately 60 patients between all of the participating centers to account for possible loss-to-follow-up (LTf).

- **Primary Endpoint**
 - 35-day sinonasal mucosal inflammation assessed by rigid endoscopy and graded on Lund-Kennedy sinus mucosal endoscopic staging system
- **Secondary Endpoints**
 - 90-day post ESS incidence of middle meatal synechiae
 - 35 and 90-day sinonasal mucosal inflammation assessed by rigid endoscopy and graded on Lund-Kennedy sinus mucosal endoscopic staging system
 - 35 and 90-day intraocular pressure (IOP) assessed using applanation tonometry and compared to baseline IOP obtained preoperatively
 - 35 and 90-day post-ESS incidence of middle meatal synechiae
 - 90-day validated Sinonasal Outcomes Test-22 (SNOT- 22) scores
 - 35-day frequency of postoperative interventions, including lyses of adhesions and debridement.
 - 35-day frequency of oral steroid rescue
 - 35 days middle turbinate position

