8.1 Inclusion Criteria

- 1) Age between 18 and 75 years

- 2) Diagnosis of chronic rhinosinusitis (CRS), per current guidelines
- 3) Patients who need to undergo primary bilateral complete endoscopic sinus surgery
- 4) Subject has the ability to follow the study instructions, is willing to be available on the specific required study visit days, and is willing to complete all study visit procedures and assessments
- 5) Subject must understand the research nature of this study and sign an informed consent prior to the performance of any study-specific procedure or assessment

8.2 **Exclusion Criteria**

- 1) Subject is pregnant or breast feeding
- 2) Patients with sino-nasal tumors
- 3) Patients solely undergoing nasal septal reconstruction
- 4) Patients with previous history of endoscopic sinus surgery
- 5) Cystic fibrosis or syndromic patients
- 6) Patients with autoimmune diseases
- 7) Patients who have taken oral steroids less than 30 days prior to surgery
- 8) Patients with a history or diagnosis of glaucoma or ocular hypertension
- 9) Any other circumstance or condition that in the Investigator's opinion causes the subject to be an inappropriate candidate for participating in this study

8.3 **Blinding**

The study is double-blinded. Each patient is his or her own control. Neither the patient nor the assessor will know on which side the respective spacer is placed. The Principal Investigator will be the blinded assessor. The choice of spacer for each side will be randomized using the sealed envelope system.

8.4 **Study Procedures**

A table of study assessments is presented in Appendix A.

8.5 **Screening/Enrollment Visit**

All consented subjects will be assigned a unique subject number. Screening procedures can occur only after consent is signed. Screening and device placement may occur on the same day. If the placement procedure occurs on a different day than the screening/enrollment visit the inclusion/exclusion criteria have to be reevaluated. The device placement attempt must occur within 30 days of initiating screening procedures.

As a standard of care, all patients will fill out the SNOT-22 quality of life questionnaire at this visit.

8.6 **Screening Procedures**

The following screening procedures will be performed before the device placement attempt is initiated:

1. Written informed consent prior to conducting any study-specific procedures
2. Demographic information
3. Targeted medical history

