8.8 Follow-up visits

There will be a total of 3 follow up visits: 6-8 days, 35 days, and 90 days after ESS. Follow-up visits will consist of appropriate standard of care treatment for subjects. At each follow-up visits a nasal endoscopy will be performed and endoscopic videos will be obtained. Any potentially device related complications will be assessed, concomitant medication will be recorded. During the follow up period, subjects may receive any medication the Investigator deems necessary. Prescription of a new medication will not exclude further participation.

As a standard of care, all patients will fill out the SNOT-22 quality of life questionnaire at their 90 day visit.

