8.9 Unscheduled Visits

It is at the discretion of the Investigator to have the subject return to the study site prior to any regular scheduled visit if, for example, the subject experienced an adverse event and/or it is in the best interest of the subject for whatever reason. Evaluation of subjects during an unscheduled visit should include a nasal endoscopy if possible. All other evaluation and testing will be decided by the investigator based on the presenting issue(s) and should be documented.

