21 APPENDIX A

SCHEDULE OF EVENTS

Assessment	Screening/ Enrolment	Treatment	Spacer Removal 6+2 days	Follow up 5± 1 weeks	Follow up 13±2 weeks
Informed Consent	X				
Eligibility Criteria	X	X*			
Demographics	X				
Pregnancy Assessment	X				
Medical History	X				
CT Scan	X				
Nasal Endoscopy	X	X	X	X	X
Endoscopic Videos Acquisition/LK score		X	X	X	X
ESS procedure and spacer placement		X			
Adverse Events/UADE		X	X	X	X
Concomitant Medications	X	X	X	X	X
SNOT-22	X				X
Frequency of events**				X	
IOP (Intra-Ocular Pressure)	X			X	X

*If treatment performed on a different day than the Screening/enrollment visit

** Data collection for frequency of post op interventions, oral steroid use and turbinate position

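### The assessor is to be blind to side, but nothing in the plan keeps early-visit video or device-use records from that person before the day-35 primary score

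*Combined protocol and SAP*

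**What the plan says.** On blinding, the synopsis states "Neither the patient nor the assessor will know on which side the respective spacer is placed" and assigns the grading: "The PI at the primary site will be the blinded assessor". Section 8.3 repeats the promise without naming a site: "The Principal Investigator will be the blinded assessor". It adds that the side for each spacer is drawn by sealed envelope.

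On what is graded, section 8 gives the primary endpoint as "35-day sinonasal mucosal inflammation assessed by rigid endoscopy and graded on Lund-Kennedy sinus mucosal endoscopic staging system". The LK endpoints use days 35 and 90 only.

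On video, the synopsis says "At each visit endoscopic videos will be collected to enable scoring, as detailed in the endpoint section below". Section 8.8 says "At each follow-up visits a nasal endoscopy will be performed and endoscopic videos will be obtained", and the first of those visits is the day 6-8 removal visit. The Appendix A row "Endoscopic Videos Acquisition/LK score" is marked at Treatment, Spacer Removal, week 5 and week 13.

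On the devices, section 7 describes a Silastic sheet 0.04 inch thick, sutured into an inverted U, and a pre-shaped, boot-shaped Restora spacer about 0.84 mm thick. Section 5 calls the two similar in thickness and area.

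On records, section 17.1 has the principal investigator keep the records of device distribution and use, and allows custody to be transferred to someone else.

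**The concern.** The primary endpoint is a graded judgement, compared between the two sides of one nose. In that design the blinding of the grader carries most of the protection against bias. It is also fragile, because identifying one spacer settles the allocation of both sides of that patient.

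The plan states the aim but gives no procedure for it after allocation. Sealed envelopes conceal the side until placement. They do not govern what the assessor sees or reads afterwards. Meanwhile the plan generates side-identifying material (possibly footage with spacers in place, and certainly device-use records) and either lists it for scoring or places it with the role that does the grading. If the assessor learned the side, expectation could favour one side in the day-35 score, and the within-patient difference would carry that shift directly. Section 12.3 accepts either a trend or a significant difference as success, so no stated threshold stands between a modest shift and a favourable conclusion.

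**Working it through.** The documents give no figure to reproduce here. The check sets the provisions side by side, with some simple arithmetic.

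1. **Who grades.** Synopsis: the PI at the primary site. Section 8.3: the Principal Investigator. The synopsis plans 2-3 centres, so the two are not identical, but both make a PI the sole named assessor.

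2. **Will early footage exist?** Yes at removal: section 8.8 requires video at every follow-up visit, and patients reach the day 6-8 visit to have the spacers taken out. At Treatment, Appendix A marks the video row and the synopsis says each visit.

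3. **Is early footage scored?** Unclear. The Appendix A row joins acquisition and LK score and marks both early visits. The synopsis ties scoring to the endpoint section, where LK endpoints fall at days 35 and 90 only, so the early marks may mean acquisition alone. On that reading the footage still exists and nothing restricts who views it.

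4. **Could a spacer be in view?** Possibly. No section says whether video is taken before or after placement, or before or after removal.

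5. **Could the devices be told apart?** Silastic thickness: 0.04 × 25.4 = 1.016 mm. Difference: 1.016 − 0.84 = 0.176 mm; 0.176 / 1.016 = 17%, Restora being the thinner. That may not be visible in place. The suture and the boot shape are the stronger described differences. Recognition is possible, not certain.

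6. **How long before the primary score?** Week 5 ± 1 is days 28 to 42. From removal on day 6-8, the gap is 28 − 8 = 20 to 42 − 6 = 36 days. The spacers are out by then, so any bias needs earlier recognition that is then linked to the same patient.

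7. **What breaks that link?** No section codes the clips, shuffles them, fixes a reading order or withholds early footage. None says whether the endpoint grade is given live or from video.

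8. **Records.** Sections 8.3 and 17.1 together give the side-blind assessor's role custody of device-use records. Section 17.1 permits a transfer but does not require one.

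9. **In-person exposure.** No section says who places or removes the spacers, or bars the assessor from doing so.

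**The case against.** The strongest reply is that harm needs a chain: footage must show a spacer, the assessor must view it before day-35 scoring, tell the devices apart in place, connect it with the same patient 20 to 36 days later, and then grade differently. The documents establish none of these steps. The promise that the assessor will not know the side is itself binding, so showing that person identifying footage would breach the protocol. A reading manual may supply the procedure. Grading by rigid endoscopy and using videos for scoring are also compatible statements.

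Most of this stands as a limit on strength. It does not remove the gap. The protocol cites no manual, and its own schedule lists an LK score at the two visits where a spacer may be seen.

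A reader might infer that the assessor will be unblinded, or that the trial is not double-blind. The documents do not support that: footage could be taken before placement and after removal, someone else could score the early visits, and section 5 calls the spacers similar in thickness and area. A reader might also want an inflated false-positive rate. None can be given for this plan, because it states no test, significance level, standard deviation or unblinded fraction.

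One further objection is fair. An assessor who places or removes spacers in person is a more direct route to unblinding than video. Video rules cannot close it, so it has to be recorded and examined in the analysis.

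**Conclusion.** The point holds as a gap between a stated promise and the planned procedures. As written, the plan can bring side-identifying video or records to the sole named assessor before the day-35 Lund-Kennedy score, and sealed envelopes do not address this. It is more than missing detail, because the scheduled early scoring and the custody of records both pull against the promise of blinding.

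The size of any bias is unknown. The conclusion assumes only that early footage may show a spacer and that the suture or shape may be recognisable; it does not assume that either occurs. The importance comes from the position of the gap, on the path to the only primary endpoint, in a subjective within-patient comparison where recognising one side reveals both. It should be corrected before endpoint scoring begins. It is not evidence that the results would be biased.

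**What to change.** Amend section 8.3 and Appendix A as follows.

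1. The endpoint LK scores at days 35 and 90 are read from the recorded videos, coded for patient and visit and in random order, before the assessor sees any placement- or removal-visit footage of those patients. Name the assessor identically in the synopsis and section 8.3. A single reader can be kept.
2. Mark the Treatment and Spacer Removal columns as video acquisition only, or score them only from footage with no spacer in view.
3. Someone other than the assessor holds the side-allocation and device-use records until scoring is locked, using the transfer that section 17.1 already allows. Keep access open for the safety assessments in sections 11.2 and 11.4.
4. Record for each patient whether the assessor placed, removed or saw the spacers, and show the primary comparison also without those patients.

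**Cost.** The videos are already collected, so the added work is coding, a reading order and a different record holder. If day-35 and day-90 clips are read together, the day-35 score waits for the later visit: 13 ± 2 weeks is 11 to 15, 5 ± 1 weeks is 4 to 6, so the delay is 11 − 6 = 5 to 15 − 4 = 11 weeks. Item 4 measures in-person exposure but does not prevent it. If the assessor treats many of the patients, the restricted comparison will rest on correspondingly fewer pairs.

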3 ABBREVIATIONS

AE	Adverse Event
CRF	Case Report Form
CRS	Chronic Rhinosinusitis
CFR	Code of Federal Regulations
FDA	Food and Drug Administration
ESS	Endoscopic Sinus Surgery
ICH	International Conference on Harmonization
ITT	Intent To Treat
MM	Middle Meatus
PP	Per Protocol
SAE	Serious Adverse Event
UADE	Unanticipated Adverse Device Effect

4 INTRODUCTION

4.1 Literature review

Endoscopic sinus surgery (ESS) is the gold standard surgical intervention for chronic rhinosinusitis that is not adequately controlled with medical therapy. Synechiae formation in the middle meatus is the most common complication of endoscopic sinus surgery (1). Synechiae describes the adhesion of two opposing mucosal surfaces in the nasal cavity that can cause scarring and obstruction of the nasal passage. Incidence of synechiae formation varies in literature and ranges between 4-35 % (2, 3, and 4). Presence of middle meatal synechiae can impair sinus drainage, promote sinusitis, and limit endoscopic visualization of the sinus cavities postoperatively. This may result in difficulty in performing postoperative routine endoscopic debridement and examination, which is paramount to a successful outcome from ESS (5).

To prevent synechiae formation, numerous studies have been published evaluating the effectiveness of absorbable and non-absorbable spacers placed in the middle meatus for 1-2 weeks postoperatively. The spacer is meant to prevent contact between the denuded surfaces of the middle turbinate and the lateral nasal wall during re-epithelialization. In general, non-resorbable spacers that have been used include sponges, cotton gauze and plastic sheets. Of these, Silastic Silicone sheets have been used in a number of hospitals across the US and Canada. Lee (6) and Baguley (7) have demonstrated the effectiveness of Silastic spacers in reducing the risk of synechiae formation to between 0-6 % (6, 7). There are also a number of resorbable spacers that are in use, which are preferred by some physicians because there is minimal need to remove the packing materials as they naturally are removed or resorbed during the healing period.

In a recent meta-analysis, Lee et al (8) has revealed that usage of middle meatal spacers (absorbable and non-absorbable) did not decrease the rate of synechiae formation to a statistically significant degree compared to not using any spacer. However, when subgroup analysis was performed, non-absorbable spacer usage demonstrated a statistically significant lower incidence of synechiae compared to no spacers (6). This can be explained in part by an inherent capability of the absorbable spacer material to degrade to smaller size particulates that, if caught in the healing tissue, could illicit local inflammatory response to slow down the healing and cause further synechiae formation. This mechanism was demonstrated by Maccabee et al (9) in a rabbit model, where fibers of the absorbable spacer became incorporated into healing mucosa and increased the extent of the inflammatory response and formation of fibrosis.

To improve outcomes, physicians have attempted to load steroids such as Triamcinolone (10, 15) and antibiotics such as Neosporin (11) into nasal packing and/or stents. However, residence of the drug in the intended treatment space is minimized as the drug, which is not bound to the spacer, quickly releases and may not remain long enough to impact inflammatory response. A Mometasone Furoate coated stent (Propel™), manufactured by Intersect ENT, is currently the only drug coated nasal stent that has a claim of longer sustained release. In a randomized, controlled, double-blind trial, Marple et al (12) found that this Mometasone Furoate steroid-eluting bio-absorbable stent could significantly improve postoperative outcomes compared to a non-steroid eluting placebo arm with the same stent. Zhao et al (13) conducted a systematic review of the efficacy of this steroid-eluting stent (Propel) vs inert (both resorbable and non-

resorbable) spacers and again confirmed that there are lower rates of synechiae formation in the steroid-eluting treatment groups. However, anecdotal evidence, based on discussion with a number of surgeons in the field, suggests that a drug-loaded resorbable spacer may be subject to the same issues as non-drug-loaded resorbable spacers, namely late stage degradation of the material that can cause a secondary spike of the inflammatory cascade, requiring additional surgical intervention to remove the remaining debris.

Therefore, it has been hypothesized that a steroid eluting non-absorbable spacer may provide optimal benefit for the patient's outcome. The Restora™ spacer is made of a biocompatible non-resorbable material that is expected to deliver up to 370 µg of Mometasone Furoate. The steroid elutes out of the spacer and onto the surrounding mucosal tissue during the 6-8 day period during which it is retained.

This study is designed to evaluate basic device usability and confirm safety and effectiveness of the Restora™ Steroid eluting spacer as compared to the standard of care Silastic Silicone spacer.

